1.3 Justification for Study Design

The doses in this study were selected based on the previous clinical data of HTD1801. Studies that have been completed abroad showed that HTD1801 had good safety and tolerability after a single oral dose of 500 mg-4000 mg in healthy subjects (HTD1801.PCT002), and multiple oral doses of 500 mg/day-2000 mg/day in hypercholesterolemic subjects (HTD1801.PCT004). The results of a single-dose Phase I clinical study in healthy Chinese subjects showed that no ≥ Grade 2 adverse events (AEs) according to the Common Terminology Criteria for Adverse Events (CTCAE) V5.0 after a single oral dose of 500 mg-2000 mg (HTD1801.PCT101). Therefore, since the daily doses of 2000 mg/day (1000 mg BID) and below are reasonable, the maximum dose selected for this study was 2000 mg/day (1000 mg BID).

As shown in the results of a randomized, double-blind, placebo-controlled Phase II clinical study (HTD1801.PCT012) in NASH patients with T2DM completed in the United States, on the basis of maintaining the original blood glucose control treatment in all subjects, the HbA1c levels were significantly decreased in both the HTD1801 500 mg BID group and the HTD1801 1000 mg BID group, i.e., after administration of HTD1801 for 18 weeks, the HbA1c levels were significantly decreased from baseline; compared with the placebo group decreased from $7.0 \pm 1.05\%$ to $7.0 \pm 1.41\%$, the HTD1801 500 mg group was decreased from $6.9\pm0.86\%$ to $6.4\pm0.65\%$ (p=0.034), and the HTD1801 1000 mg group was decreased from $7.4\pm1.14\%$ to $6.7\pm1.27\%$ (p=0.004), showing a significant dose-dependence. Since there are no restrictions on the use of hypoglycemic drugs in subjects, and the expected effective dose of HTD1801 is 1000 mg/day (500 mg BID), the minimum dose of 1000 mg/day (500 mg BID) was selected in this study.

Referring to the clinical routes of administration for BBR and UDCA, and the route of administration in NASH subjects with T2DM established in the United States, the dosing regimen

of BID with meals was applied in this study.

According to the Guidelines for Clinical studies of Drugs and Biologicals for the Treatment of Diabetes Mellitus [22], the primary efficacy endpoint in this study was the change in HbA1c from baseline with 12-week treatment. When the scheduled exploratory Phase II clinical study was initiated, guidelines recommend designing an introduction period prior to randomization for education and optimization of dietary and exercise adherence of diabetes mellitus patients. Considering the stability of metabolic control parameters, a 4-week single-blind introduction period was set in this study to accurately evaluate the efficacy of the drug at different doses. In addition, salvage therapy and treatment of hypoglycemia events were determined in accordance with diabetes mellitus-related guidelines and clinical guidelines.

Protocol No.: HTD1801.PCT103

Intestinal flora is the main environmental factor affecting metabolic diseases, and participates in maintaining and regulating the host energy metabolism and immune function. Intestinal flora imbalance may lead to the occurrence and development of chronic diseases, including obesity and diabetes mellitus. In addition, the intestinal flora plays an important role in drug metabolism and can produce metabolites with different activities. Studies are carried out on the changes in intestinal flora with drug intervention to analyze its correlation with diabetes mellitus, which will help to discover the effective components or component groups with definite effects and clear mechanisms of the investigational drug, thereby benefiting the development of new drugs.

1.4 Risk Benefit Assessment

The non-clinical toxicology study on HTD1801 was completed to support this study, including repeated-dose toxicology study, reproductive toxicity study, preliminary carcinogenicity study, preliminary assessment on drug interactions, etc. The results showed good safety and tolerability of HTD1801.

At present, the pharmaceutical study and production of HTD1801 are carried out in accordance with relevant guidelines and regulations with controllable quality. In addition, based on the obtained preclinical study results, it is reasonable to expect that HTD1801 will not cause any unknown or uncontrollable toxic reactions in human. According to the completed phase I clinical studies (HTD1801.PCT002 and HTD1801.PCT004), the drug-related adverse reaction was gastrointestinal discomfort. Drug-related adverse reactions in HTD1801.PCT002 were gastrointestinal discomfort (nausea and abdominal pain); the most common treatment-emergent adverse event (TEAE) in HTD1801.PCT004 study was headache, which may not be related to the investigational drug as judged by the investigator; the severity of the above-mentioned AEs was mostly slight/mild. Two TEAEs were reported in the high-dose group of HTD1801.PCT004: cholecystitis and hepatitis; these two SAE were moderate in intensity and not related to the investigational drug as judged by the investigator.

The completed phase I studies showed good safety and tolerability of HTD1801 in healthy subjects at single oral doses up to 4000 mg, and in subjects with hypercholesterolemia at multiple oral doses up to 2000 mg/day for 28 days. The completed phase II study showed good safety and tolerability of HTD1801 in adult T2DM patients with NASH and adult patients with PSC at multiple oral doses up to 2000 mg/day for 18 weeks. No investigational drug-related SAE were reported (see the Investigator's Brochure for details).

HTD1801 is an ionic salt formed by BBR and UDCA. Both BBR and UDCA have a long history of clinical use in traditional and modern medicine in different countries, with abundant clinical literatures, and their safety is known and controllable. According to previous reports in the literatures, the safety of UDCA has been widely recognized; while BBR has two potential safety issues: exacerbation of jaundice and kernicterus in neonates with glucose-6-phosphate dehydrogenase (G6PD) deficiency, as well injury to the developing fetus in the placenta. BBR can

also be passed through breast milk, which raises some concerns about using BBR while breastfeeding.

Protocol No.: HTD1801.PCT103

For "exacerbation of jaundice and kernicterus in neonates with G6PD deficiency", the clinical indication of HTD1801 is for adult subjects only, so this safety risk dose not exist. In addition, the inclusion/exclusion criteria for the clinical study clearly stipulated those subjects who have any disease that may cause hemolysis or unstable red blood cell count and affect the HbA1c test, such as hemolytic anemia, etc., should not be included in this study.

Based on the results of previous studies, in the clinical studies of HTD1801 completed in the United States, Australia and Canada, the maximum dosing duration are 18 weeks, and female subjects of childbearing potential were included. No drug-related SAEs were observed in these studies. Although developmental toxicity that may cause concern has not been detected in the reproductive toxicity studies that have been completed so far, in order to further ensure the medication safety of subjects, it is necessary to definitely control reproductive risks in the clinical study protocol, including but not limited to the following:

- a) Pregnant or lactating female subjects should be excluded; female subjects of childbearing potential are eligible for inclusion in this study only if they are negative in the pregnancy test at screening (V1) and before randomization (V3);
- b) Subjects should be strictly screened and take contraceptive according to the study protocol; if the partners of the male subjects or the female subjects are planning to become pregnant, or are unwilling to take reliable contraceptive measures (see APPENDIX 6) during the period from the signing of the informed consent forms (ICFs) to 3 months after the last dose of the investigational drug, the subjects should be excluded;
- c) Pregnancies in female subjects of childbearing potential should be followed up throughout the study.

In the inclusion criteria, subjects with hyperglycemia and/or severe acute and chronic complications of diabetes mellitus and severe comorbidities in other organ systems are excluded. During the study, subjects will undergo self-monitoring of blood glucose (SMBG) in addition to following lifestyle intervention requirements and receiving continuous treatment. During the study, the principles of salvage therapy and hypoglycemia event treatment were set up. Subjects with hyperglycemia and repeated episodes of severe hypoglycemia that could not be controlled by salvage therapy can withdraw from the study in advance according to the withdrawal criteria to ensure the safety of the subjects to the greatest extent.

2. STUDY OBJECTIVES

2.1 Primary Objective

To evaluate the effect of HTD1801 on glycemic control in T2DM patients.

2.2 Secondary Objectives

- 1. To evaluate the safety of HTD1801 in T2DM patients.
- 2. To evaluate the effect of HTD1801 on improving IR.
- 3. To evaluate the effect of HTD1801 on fatty liver-related indicators such as liver fat, AST, ALT, ect.

Protocol No.: HTD1801.PCT103

- 4. To evaluate the effect of HTD1801 on metabolism-related indicators such as body weight, blood lipids, etc.
- 5. To evaluate the PPK profiles of multiple-dose HTD1801 in T2DM patients, and to provide a reference for determination of the dose in follow-up clinical studies.
- 6. To evaluate the effect of multiple-dose HTD1801 on the intestinal flora characteristics, and the possible pharmacological effects by acting on the intestinal flora.

3. SUBJECT SELECTION AND WITHDRAWAL

3.1 Inclusion Criteria

Subjects who meet all the following criteria will be included in this study:

1. Male or female subjects who are 18 (inclusive) to 75 (inclusive) years old when signing the ICFs.

Protocol No.: HTD1801.PCT103

- 2. Subjects who are diagnosed as T2DM according to the WHO criteria 1999.
- 3. Subjects who have received diet and exercise treatment for ≥ 8 weeks prior to screening.
- 4. Subjects whose HbA1c must meet the following criteria:
 - (1) Screening (V1) HbA1c: 7.5%≤HbA1c≤11.0% (local laboratory);
 - (2) Pre-randomization (V3) HbA1c: 7.0%≤HbA1c≤10.5% (central laboratory).
- 5. Subjects whose fasting blood glucose must meet the following criteria:
 - (1) Screening (V1) fasting blood glucose: <13.9 mmol/L (if the plasma glucose cannot be detected in the local laboratory, the serum glucose result can be accepted);
 - (2) Pre-randomization (V3) fasting plasma glucose (FPG): <13.9 mmol/L (central laboratory)
- 6. At screening, the BMI is within the range of 18-40 kg/m² (inclusive).
- 7. Subjects who agree to maintain the same dietary and exercise habits throughout the study, and are willing and able to properly use a home blood glucose meter for SMBG and record.
- 8. Subjects who are able to understand and willing to sign the written ICFs and comply with the study protocol.

3.2 Exclusion Criteria

Subjects who meet any one of the following criteria will be excluded from this study:

- 1. Subjects who have Type 1 diabetes mellitus (T1DM), or specific diabetes mellitus (such as diabetes mellitus due to pancreatic injury, Cushing's syndrome or acromegaly, etc.).
- 2. Subjects who have diabetic ketoacidosis or hyperosmolar hyperglycemic state within 6 months prior to screening.
- 3. Subjects who have proliferative retinopathy or macular degeneration, severe diabetic neuropathy, diabetic foot, or intermittent claudication within 6 months prior to screening which are unstable and require treatment.
- 4. Subjects who have the history of ≥2 episodes of Grade 3 hypoglycemia within 12 months prior to screening (see Section 3.3.1.1 for the definition of hypoglycemia).
- 5. Subjects who have any disease that may cause hemolysis or erythrocyte instability and affect the HbA1c test, such as hemolytic anemia, etc., at screening (V1).
- 6. Subjects who have the weight changes (gain or loss) \geq 5% before randomization (V3) compared with those at screening (V1).
- 7. Subjects who have the liver stiffness measurement (LSM) >13.0 kPa measured by liver

- transient elastography at screening (V1).
- 8. Subjects who have used any chemical or traditional Chinese medicines containing UDCA or BBR within 4 weeks prior to screening.

Protocol No.: HTD1801.PCT103

- 9. Subjects who are known to be allergic to the active ingredients of the investigational drug (HTD1801, BBR, UDCA) or its excipients; or known to be allergic to the salvage drug Empagliflozin or related excipients.
- 10. Subjects who have the history of drug abuse or dependence within 12 months prior to screening.
- 11. Subjects who have the refractory urinary tract or genital infection within 6 months prior to screening.
- 12. Subjects who have severe gastrointestinal diseases at screening (V1) that affect drug absorption, distribution, metabolism, and excretion, including chronic gastrointestinal disease that causes recurrent diarrhea (such as irritable bowel syndrome, ulcerative colitis, Crohn's disease, etc.); or have undergone gastrointestinal surgery that affects drug absorption, such as gastrostomy, anastomosis, or intestinal resection.
- 13. Subjects who have used insulin or its analogs for more than 2 consecutive weeks within 12 months prior to screening (use of insulin or its analogs for hyperglycemia during pregnancy prior to screening is not within the scope of this limitation);
- 14. Subjects who have used ≥2 types of hypoglycemic drugs with different mechanisms prior to screening for more than 8 weeks and within 12 months (use of insulin or its analogs for hyperglycemia during pregnancy prior to screening is not within the scope of this limitation).
- 15. Subjects who have used any drugs that may affect blood glucose metabolism within 8 weeks prior to screening, such as hypoglycemic drugs (including traditional Chinese medicines indicated for hypoglycemic therapy), systemic glucocorticoids (except for inhalation, eye instillation, and topical skin drugs), growth hormone, non-selective β-receptor blockers (such as propranolol, etc.), thiazide diuretics at a dose of >25 mg/day or aspirin at a dose of >300 mg/day, etc.
- 16. Subjects who have used liver-protecting drugs (including traditional Chinese medicine) or dietary supplements within 4 weeks prior to screening (see APPENDIX 1).
- 17. Subjects who have used any chemical drugs, traditional Chinese medicines or dietary supplements for weight loss (see APPENDIX 2), participated in a weight loss program, or followed a special diet within 4 weeks prior to screening.
- 18. Subjects who have used antibiotics (except for topical application) within 4 weeks prior to screening.
- 19. Subjects who have been administered with probiotic-containing drugs or dietary supplements within 4 weeks prior to screening or prior to randomization (V3) (see APPENDIX 3).
- 20. Subjects who have used lipid-lowering drugs at stable doses <4 weeks prior at screening (V1).
- 21. Subjects who have uncontrolled hypertension (systolic blood pressure >160 mmHg and/or diastolic blood pressure >100 mmHg) at screening (V1) or before randomization (V3).

22. Subjects who have abnormal thyroid function that cannot be controlled with drugs at stable doses, or clinically significant abnormality in thyroid function test results that requires drug treatment at screening (V1).

Protocol No.: HTD1801.PCT103

- 23. Subjects who have suffered from severe infection (such as acute pancreatitis, COVID-19) or severe trauma, or have undergone major surgery within 3 months prior to screening and are judged to be inappropriate to participate in this study by the investigator.
- 24. Subjects who have the history of the following acute or chronic liver diseases at screening (V1): autoimmune hepatitis, primary biliary cholangitis, alcoholic liver disease, hepatolenticular degeneration, or drug-induced liver injury.
- 25. Subjects who have the history of malignant tumors within 5 years prior to screening (except for cured basal cell carcinoma of the skin, carcinoma cervix in situ), or being assessed for potential malignant tumors at screening (V1).
- 26. Subjects who have the history of psychiatric diseases or are receiving drug treatment, and are judged to be inappropriate to participate in this study by the investigator at screening (V1).
- 27. Subjects who have had the following history within 12 months prior to screening: Decompensated heart failure (New York Heart Association [NYHA] Class III or IV), unstable angina, myocardial infarction, percutaneous coronary intervention, coronary bypass transplantation, hemorrhagic stroke, and ischemic stroke (except lacunar infarction).
- 28. Subjects who have clinically significant abnormalities in 12-lead ECG and require treatment or close follow-up (such as Grade II or III atrioventricular block, atrial fibrillation, atrial flutter, pre-excitation syndrome, etc.) at screening (V1); or QT interval corrected by Fridericia formula (QTcF) > 470 ms (male) or QTcF > 480 ms (female) (see APPENDIX 5 for the calculation formula) at screening.
- 29. Etiological test at screening (V1): positive for hepatitis B surface antigen and hepatitis B viral load (HBV-DNA) above the lower limit of detection of the local laboratory; or positive for anti-hepatitis C antibody and hepatitis C viral load (HCV-RNA) above the lower limit of detection of the local laboratory; or positive for treponema pallidum antibody (TP-Ab); or positive for human immunodeficiency virus antibody (HIV-Ab).
- 30. Subjects whose laboratory parameters are within any of the following ranges at screening (V1):
 - ALT \geq 5×ULN, AST \geq 5×ULN;
 - ALP $> 2 \times$ ULN:
 - DBIL> 1.5× ULN;
 - TBIL> 1.5× ULN;
 - Serum TG \geq 4.52 mmol/L (400 mg/dL), or serum LDL-C \geq 5.69 mmol/L (220 mg/dL);
 - Hemoglobin <1 ×LLN;
 - eGFR < 60 mL/min/1.73 m² (see APPENDIX 5 for calculation formula); or urine protein \geq ++.
- 31. Subjects who have donated blood or had massive blood loss (≥ 400 mL), or received

blood transfusion or blood products within 3 months prior to screening.

32. Subjects who are alcoholism (14 units of alcohol per week: 1 unit = 285 mL beer, or 25 mL liquor, or 100 mL wine) within the 12 months prior to screening and are unable to control alcoholism during the study.

Protocol No.: HTD1801.PCT103

- 33. Pregnant or lactating female subjects.
- 34. Partners of the male subjects or the female subjects are planning to become pregnant, or are unwilling to take reliable contraceptive measures (see APPENDIX 6) during the period from the signing of the ICFs to 3 months after the last dose of the investigational drug.
- 35. Subjects who have participated in clinical studies on other investigational drugs or medical devices, and taken investigational drugs or used medical devices, or used any unapproved treatment methods within 3 months prior to screening.
- 36. Subjects who have received vaccines (except inactivated vaccines) within 4 weeks prior to screening or planned to receive the vaccines (except inactivated vaccines) during the study (from the signing of the ICFs to the end of the safety follow-up visit).
- 37. Subjects who have the medication compliance <80% or >120% in the single-blind introduction period.
- 38. Subjects who are considered as not suitable for participating in the study by the investigator due to other conditions.

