6. CONCOMITANT/PROHIBITED MEDICATIONS AND TREATMENT

6.1 Concomitant Medication

6.1.1 Allowed concomitant medications/treatment:

Without the consent of the investigator, no other hypoglycemic drugs other than the investigational drug can be used throughout the study, except for the drugs used for the treatment of AEs. Concomitant drugs (such as antihypertensive, lipid-lowering drugs) before the study should continue to be used at their original doses, and the reasons for their use should be fully recorded in the eCRF. Any new concomitant medications/treatments, or changes in concomitant medication doses, and the reason for medication, dates of administration (including start and end dates), and dosing information (including dose, route, frequency) must be recorded in the corresponding section in the eCRF from the signing of the ICFs through the entire treatment phase and during the safety follow-up visit.

Protocol No.: HTD1801.PCT103

6.1.2 Prohibited concomitant medications/treatment:

The following limitations on prohibited concomitant treatments or drugs do not apply to the salvage therapy administered to subjects by the investigator according to the protocol (see Section 5.1.3.3). During the period from the subject signs the ICFs to the end of the double-blind phase (excluding the safety follow-up visit phase and early withdrawal visit), the prohibited concomitant treatments include:

- Any drugs that may affect blood glucose metabolism, such as:
- Hypoglycemic drugs (including traditional Chinese medicines indicated for hypoglycemic therapy)
- Systemic glucocorticoids (except inhalation, eye instillation, and topical dermal application)
- Growth hormone
- Non-selective β-receptor blockers (such as propranolol, etc.)
- Thiazide diuretics at a dose > 25 mg/day
- Aspirin at a dose >300 mg/day
- Thyroid hormones: During the study, no new thyroid hormone drugs or changes in the previous drug regimen (except stable replacement therapy) are allowed.
- Liver-protecting drugs (including traditional Chinese medicine) or dietary supplements (see APPENDIX 1)
- Any chemical drugs, traditional Chinese medicines or dietary supplements for weight loss (see APPENDIX 2), a weight loss program, or a special diet.
- robiotic-containing drugs or dietary supplements (see APPENDIX 3).
- New use of drugs for controlling blood lipid and blood pressure, or changes in previous drug regimens
- Blood transfusion or use of blood products is required.

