- Vaccines (except for inactivated vaccines).
- Drugs or treatments that, in the judgment of investigators, may affect the objectivity of the assessment of safety and/or efficacy of subjects in this study.

• Traditional Chinese Medicine.

Unless in emergencies, subjects are prohibited from using any new drug that is not reported during the screening phase without prior consultation with the investigator or self-adjusting the dose of concomitant drugs during the study. In emergencies, if there is a clinical indication for the use of a new drug or dose modification of the concomitant drug, the subject must notify the investigator before using the concomitant drug. The investigator will determine and record any emergency medication's usage, name, dose, route of administration, objectives of treatment, and date of administration.

Protocol No.: HTD1801.PCT103

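### The antibiotic exclusion stops at screening, about 4 to 6 weeks before the baseline flora samples, while the matching probiotic rule runs up to and beyond randomization (minor)

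*Protocol*

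**What the plan says.** Secondary objective 6 (Protocol 2.2) is "To evaluate the effect of multiple-dose HTD1801 on the intestinal flora characteristics, and the possible pharmacological effects by acting on the intestinal flora". It is measured by secondary endpoints 16 and 17 (section 7.2), the changes from baseline in flora and in flora metabolites at Weeks 8 and 12. Feces (where available) and metabolomics serum are collected at V4 (Day 1), V6 (Week 8) and V7 (Week 12), and also at a pre-salvage visit.

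Antibiotics are restricted by name in one criterion only, exclusion 18 of section 3.2, which the synopsis repeats: "Subjects who have used antibiotics (except for topical application) within 4 weeks prior to screening". Exclusion 19 directly below it adds a second anchor for probiotics: "Subjects who have been administered with probiotic-containing drugs or dietary supplements within 4 weeks prior to screening or prior to randomization (V3".

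Section 6.1.2 prohibits listed treatments "During the period from the subject signs the ICFs to the end of the double-blind phase". The list includes "robiotic-containing drugs or dietary supplements" (the first letter is missing in the text) and does not mention antibiotics. Two general clauses in the same section could reach them. One prohibits "Drugs or treatments that, in the judgment of investigators, may affect the objectivity of the assessment of safety and/or efficacy". The other says that, outside emergencies, "subjects are prohibited from using any new drug that is not reported during the screening phase without prior consultation with the investigator".

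The flora analysis itself is deferred to a separate plan (section 10.4.8), which is not at hand.

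**The concern.** Antibiotics and probiotics are neighbouring exclusions with the same 4-week window, but only the probiotic rule extends to the period in which flora is sampled. A subject can pass screening, take an antibiotic course during the run-in, and be randomized with no named criterion breached. The eligibility review at V4 need not catch it, because exclusion 18 looks back only from screening.

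What is at stake is the quality of a change-from-baseline measure. A course shortly before V4 disturbs the baseline, and that one disturbed value enters both the Week 8 and the Week 12 change. A course shortly before V6 or V7 disturbs that visit's change. Section 1.2.2.1 lists antibacterial action among the mechanisms of berberine, so an antibiotic effect on flora could resemble the drug effect being looked for.

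**Working it through.** **1. Rules side by side**

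| Period | Probiotics | Antibiotics (non-topical) |
|---|---|---|
| 4 weeks before screening | Excluded (no. 19) | Excluded (no. 18) |
| Look-back from randomization (V3) | Excluded (no. 19) | No named rule |
| Consent to end of double-blind phase | Prohibited by name (6.1.2) | Not named; general clauses only |

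Of the six consecutive drug-use exclusions 15 to 20, five have a named counterpart in section 6.1.2: glucose-affecting drugs (15), liver-protecting drugs (16), weight-loss products (17), probiotics (19) and lipid-lowering drugs (20). Antibiotics (18) have none.

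**2. Timing** (phase lengths from section 4.1)

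- Screening is up to 14 days, the run-in 28 days and treatment 84 days.
- From the end of the antibiotic window (V1) to the baseline sample (V4): 28 days at the shortest, 14 + 28 = 42 days at the longest, so about 4 to 6 weeks.
- From V1 to the Week 8 sample: about 12 to 14 weeks. From V1 to the Week 12 sample: about 16 to 18 weeks.
- Longest span with no named antibiotic rule: 42 + 84 = 126 days (18 weeks).

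**3. Number of subjects affected.** The documents give no rate of antibiotic use, so this rests on assumptions: 5-15% of subjects have one course in the 126 days, course end dates are spread evenly, and a sample counts as affected if it is taken within 28 days after the course.

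- Subjects with any course: 0.05 × 99 = 4.95 to 0.15 × 99 = 14.85, so about 5-15.
- Days on which a course can affect a sample: 28 before V4, 28 before V6 and 28 before V7, in total 84.
- Share of the span: 84/126 = 2/3. Courses ending in Days -42 to -28, or in roughly Days 1 to 28, affect none of the three samples.
- Subjects with an affected sample: 4.95 × 2/3 = 3.3 to 14.85 × 2/3 = 9.9, so about 3-10 of 99, or about 1-3 per arm of 33.
- Of these, subjects with an affected baseline: 4.95 × 28/126 = 1.1 to 14.85 × 28/126 = 3.3, so about 1-3 of 99.

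**4. Would copying exclusion 19's wording be enough?** V3 is at Day -7 to Day -5 (section 4.3.3). A look-back anchored at V3 would leave the 5 to 7 days directly before the V4 sample open. For probiotics section 6.1.2 closes that interval. For antibiotics nothing named does.

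**The case against.** Four arguments weigh against the point.

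*The trial is randomized against placebo.* A reader might infer that the flora results could show antibiotic courses and not HTD1801. The documents do not support that for the between-arm comparison. Courses before randomization are balanced across arms in expectation, so they cost precision and allow chance imbalance but add no systematic bias. Bias needs use after randomization to differ by arm, and nothing in the protocol shows that it will. Within-arm change from baseline is affected directly. This objection stands and limits the point.

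*Control exists, although it is discretionary.* The two general clauses in section 6.1.2, and exclusion 38, let an investigator disallow a drug or a subject. So antibiotics are not freely permitted; they are only not named. But these clauses mention neither antibiotics nor flora, can be applied differently across about 14 sites, and were not considered sufficient for probiotics. Leaving antibiotics off an absolute prohibition list is defensible because infections need treatment. That reason does not explain why eligibility is not checked again before randomization.

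*The separate flora plan may handle affected samples.* It may, and its absence here is no fault. Section 6.1.1 requires the reason, dates and dosing of new concomitant medication to be recorded from consent onwards, so courses can be identified. An analysis plan cannot change eligibility or restore a disturbed baseline.

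*The protocol never says why exclusion 18 is there.* Correct. That it serves to protect the flora endpoints is an inference from its place next to the probiotic rule and from objective 6.

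**Conclusion.** The point holds as a minor inconsistency between exclusion 18, exclusion 19 and section 6.1.2. A systemic antibiotic course in the run-in breaches no named criterion, although the baseline flora and metabolomics samples follow V1 by about 4 to 6 weeks. The main effect is noise, chance imbalance in small arms and distorted within-arm change, all confined to secondary endpoints 16 and 17. The HbA1c analysis does not depend on this rule.

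The estimate of 3-10 of 99 subjects rests on the assumed 5-15% rate, evenly spread courses and the 4-week carry-over. A reader might take all 5-15 subjects with a course as affected, but about a third of the 126 days lie too far ahead of any sample for that. Because feces are collected only where available, fewer stool samples may be affected. The inconsistency itself is read from the text and does not depend on the rate.

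**What to change.** Reconcile exclusion 18 with exclusion 19 and section 6.1.2, in the synopsis as well, so that the antibiotic look-back also applies before randomization and reaches the V4 baseline sample. A V3 anchor alone is not enough: the eligibility review at V4 should also ask about the days since V3. The change should not restrict treatment of infection at any time.

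Use the concomitant-medication records to flag flora and metabolomics samples taken after a systemic course. If the separate flora plan does not already contain one, add a sensitivity analysis that omits the flagged samples. All samples stay in the main flora comparison unless that plan says otherwise.

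The cost is one clause in exclusion 18, a few more run-in failures (about 1-3 per 99 subjects under the same assumptions) and a little more analysis work.
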